3.8 Visit Windows

3.8.1 Definition of Study Day

Study day is the day relative to the treatment of the first eye. Study day for events on or after the date of the first dose will be defined as the number of days from the date of the first dose of study drug, plus 1 day, so that the date of the first dose will be defined as Day 1.

3.8.2 Definition of Study Baseline

Study baseline is defined as the last observation obtained on or prior to the start of the procedure on the first eye on Study Day 1.

Change from baseline is defined as post-baseline assessment minus baseline assessment. Baseline value will not be carried forward to impute the post-baseline values.

For efficacy measures performed on individual eyes, baseline will be determined for each eye separately based on the date of the procedure on each particular eye.

3.8.3 Analysis Visits

The CRF nominal study visits will be used to define analysis visits for each eye based on the expected number of months post-procedure. This allows analysis visits to represent the number of months of post-procedure follow-up associated with each eye.

3.8.4 Selection of Data in the Event of Multiple Records in a Visit

If multiple assessments fall within the same analysis visit, the assessment closest to the target visit day specified in the protocol study procedures will be used. If two assessments are equidistant from the target visit day, the earlier assessment will be used.

3.8.5 Rounding

The method of rounding for data presentation is provided in Appendix D.

4. BASELINE CHARACTERISTICS AND SUBJECT DISPOSITION

Descriptive baseline summaries of continuous data will present the group mean, standard deviation, median, minima, and maxima. Descriptive summaries of discrete data will present the category counts as frequencies and percentages.

Summaries will be presented by treatment as recorded on the CRF. Any results presented by diagnosis will be based on diagnosis from medical history.

4.1 Disposition of Subjects

A disposition summary will include

- Number of randomized and treated by primary and fellow eye
- Number of subjects in the Safety analysis set. Subjects may be included in more than one column of the second eye was treated under a different treatment group.
- Number and percentage of subjects with the procedure on the right eye (OD), the left eye (OS) or both eyes (OU) for initial treatment
- Number and percentage of patients that had subsequent CXL treatment on the fellow eye
- Number and percentage of subjects in the efficacy analysis set (EAS)
- Number and percentage of subjects ongoing (per protocol)
- Number and percentage of subjects completing study (at Month 6 per protocol)
- Number and percentage of subjects discontinuing study and the reasons for discontinuation

A subject will be considered discontinued if they have a record that from the end of study CRF page suggesting they did not complete study.

Disposition summaries will be presented by initial treatment received and diagnosis. Percentages will be based on the number of subjects randomized.

A listing of subject disposition will include the date of the procedure for each eye, study completion status, and reason for termination (if applicable).

A separate listing will be provided to identify patients that had re-treatment with CXL.

4.2 Demographics and Baseline Characteristics

Demographic and baseline characteristics summaries, for subjects in the randomized analysis set, will include:

- Age (years at baseline)

- Sex
- Race
- Ethnicity

Demographic and baseline characteristics will be summarized by randomized treatment group for the Treated Analysis Set. No statistical comparisons between the treatment groups will be conducted.

4.3 CXL Procedures

Frequency counts of patients treated with one eye (OS, OD) and with both eyes (OU) will be provided by diagnosis and by randomized treatment group. Continuous statistics for the number of minutes required to achieve corneal saturation with Riboflavin solution for each eye (OS, OD) will also be provided.

4.4 Inclusion and Exclusion Criteria

Data for inclusion and exclusion criteria will not be presented.

4.5 Medical History

Medical history data is used for identification of various subsets of patients but will not be summarized or listed.

4.6 Prior and Concomitant Medications

Prior and concomitant medications will be coded using the World Health Organization (WHO) drug dictionary.

Prior medications are defined as any medications that started and stopped prior to the first dose administration on Study Day 1. Concomitant medications are defined as any medications that started or ongoing at time or after the first dose administration on Study Day 1 in each of the study phase.

Where a medication recorded with a partially or fully missing start/stop date or time, and it is unclear as to whether the medication is concomitant, it will be assumed that it is concomitant. Rules for date imputation for classification as prior and/or concomitant are found in Appendix C.

Prior and concomitant medications may be summarized in ad hoc manner.

5. EFFICACY

Efficacy analysis will be performed using the EAS analysis set. All analysis will be based on a change from baseline in the Primary Eye. Point estimates and 95% confidence intervals (CIs) for the mean changes from baseline within each treatment group will be presented.

Only the required CRF nominal study visits (Month 3, Month 6, Month 12) will be used for efficacy analyses of changes from baseline. Analysis will be repeated for both the Primary eye and the Fellow eye. Analysis will be based on months of post-procedure follow-up for the eye being summarized.

Optional visits other than month 12 and unscheduled visits will not be used.

5.1 Primary Efficacy Endpoint

The primary measure of efficacy is the mean change from baseline in LogMAR of Corrected Distance Visual Acuity (CDVA) in the Primary Eye at Month 12 for each treatment group. As supportive analysis to the primary endpoint, the mean change from baseline and treatment differences will be estimated at Month 3 and Month 6.

Separately for each timepoint, analysis of variance (ANOVA) will be used to obtain point estimates and CIs for the change from baseline in LogMAR CDVA for each group. ANOVA will also be used to obtain point estimates and CIs for all pairwise comparisons between the treatment arms. P-values may be provided for descriptive purposes only.

As a sensitivity analysis, separate point estimates and confidence intervals for treatment differences based on a two-sample t-tests for each pairwise comparison will be performed without assuming equal variances. Satterthwaite approximation for degrees of freedom will be used.

Other sensitivity analysis such as mixed models repeated measures to account for the longitudinal nature of the data may be considered in an ad hoc manner.

The primary analysis will be repeated for the Fellow eye.

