8.1 EFFICACY ENDPOINTS

The primary efficacy endpoint of this trial is change in corrected distance visual acuity (CDVA) at the last required study visit (6 months post-op), compared to baseline. CDVA will be evaluated by an observer who is masked to the treatment protocol to which study subjects have been assigned. All eyes treated (single or both eyes of an individual subject) will be included in the analysis of efficacy.

The Secondary Endpoints will be:

1. Change in UCVA at 6 months, compared to baseline.
2. Change in K_{\max} , compared to baseline.

Additional analyses will be performed in subgroups of patients using standard statistical stratification methods, including patients over the age of 35, patients under the age of 18, disease severity, and patients with and without pre-procedure corneal scars. Results in male vs. female patients and post LASIK ectasia vs. primary keratoconus will also be evaluated.

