1.1 Study Design

Approximately 3,000 eligible subjects presenting with asymmetric corneas will be enrolled at 21 clinical sites.

The planned primary effectiveness analysis will be based on 6-month post-procedure assessments. Subjects will be assessed post-procedure day 1, at 3 months and at 6 months. Visual acuity measurements and full ocular assessments (manifest refraction with CDVA, UCVA, slit lamp biomicroscopy including a rating of corneal haze, pachymetry, Pentacam corneal tomography, IOP) will be performed during that period.

According to the protocol, Optional 1 week, 1-2 month, 12-month, 24-month, and 36-month assessments will also be performed, at the discretion of the physician. The 1-2 month visit may occur if the subject experiences changes in refractive error, and requires a new prescription for spectacles or contact lenses.

In order to provide 12-month data to FDA for Phase 3 planning, sites were instructed to contact patients to request a 12-month assessment. In these cases, patients may have a 6-month visit that suggests they completed study, yet still return for the 12-month assessment. Not all patients that completed study at the 6-month visit will return for a 12-month assessment.

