1.6 Changes from Protocol

The protocol states the primary efficacy endpoint of this trial is change in corrected distance visual acuity (CDVA) at the last required study visit (6 months post-op), compared to baseline. For this analysis, the change in CDVA will be estimated at Month 6 as well as Month 12.

The protocol also states that two-sample t-tests will be used for treatment comparisons. Since there are three treatment groups, analysis of variance (ANOVA) will be used instead of conducting separate t-tests on each pairwise combination of treatments. Separate t-tests on each pairwise comparison will be performed as a supportive analysis.

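### SAP 5.1 makes the optional Month 12 visit the primary CDVA timepoint, other SAP sections do not declare this, and no planned method deals with patients who do not return

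*SAP*

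**What the plan says.** **Which timepoint is primary**

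- Protocol 8.1: the primary endpoint is "change in corrected distance visual acuity (CDVA) at the last required study visit (6 months post-op), compared to baseline". SAP 1.1 likewise bases the planned primary effectiveness analysis on the 6-month assessments.
- SAP 1.2.1: the primary objective names Months 6 and 12 and does not rank them.
- SAP 1.3.1: the primary endpoint is LogMAR CDVA, with no timepoint.
- SAP 1.6, the SAP's current list of departures from the protocol: "For this analysis, the change in CDVA will be estimated at Month 6 as well as Month 12".
- SAP 5.1: the primary measure is "the mean change from baseline in LogMAR of Corrected Distance Visual Acuity (CDVA) in the Primary Eye at Month 12". It then adds: "As supportive analysis to the primary endpoint, the mean change from baseline and treatment differences will be estimated at Month 3 and Month 6".

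**Status of the Month 12 visit**

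- Protocol 5.4 and SAP 2 make every visit after Month 6 optional. Sites were asked to contact patients and request the 12-month assessment.
- SAP 1.1 concedes: "Not all patients that completed study at the 6-month visit will return for a 12-month assessment".
- SAP 5 nevertheless limits the efficacy analyses with the words "Only the required CRF nominal study visits (Month 3, Month 6, Month 12", where the list ends. A later sentence in the same section treats Month 12 as one of the optional visits.

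**Handling of absent values**

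- SAP 3.6 imputes nothing and says the EAS definition rules out missing primary data.
- SAP 3.2.3 admits a patient to the EAS on a change value in any one of the three efficacy endpoints and names no visit.
- SAP 5.1 runs ANOVA separately at each timepoint. A repeated-measures model is mentioned only as a possible ad hoc sensitivity analysis.

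**The concern.** There are two linked problems.

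The first is labelling. A reader who relies on SAP 1.6 learns that Month 12 has been added beside Month 6. Only SAP 5.1 shows that Month 6 has become supportive. Results could be reported as primary at either month, and either choice could be defended from the text.

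The second is estimation. The visit that SAP 5.1 puts first is one that patients were free to skip. A per-visit ANOVA without imputation describes whoever came back. Those means and intervals are meant to support a Phase 3 design and a meeting with FDA. If return is related to outcome, the effect size carried into Phase 3 is shifted. The statement that primary data cannot be missing would keep readers from looking for the problem.

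**Working it through.** **1. Does the governing clause settle the timepoint?** SAP 1 says the SAP prevails where it and the protocol disagree. That resolves SAP 5.1 against Protocol 8.1. It does not resolve SAP 5.1 against SAP 1.1, 1.2.1 and 1.6, which are in the same document. The SAP cites protocol version 4.3, and the protocol reviewed here is Revision 04.1. The comparison does not depend on that, because SAP 1.6 itself restates the protocol endpoint as Month 6.

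**2. Does the EAS definition rule out missing primary data?** Take a keratoconus patient who meets the other EAS criteria and whose only change value is Kmax at Month 3. SAP 3.2.3 admits this patient, who has no Month 12 CDVA. The statement in SAP 3.6 therefore does not follow. SAP 1.4 further limits efficacy to patients enrolled long enough to be due a Month 12 visit. That removes patients who could not yet have attended, but not those who were due and did not come.

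**3. What the Month 12 estimate uses.** With a separate ANOVA and no imputation, it uses only eyes with a Month 12 CDVA. Month 3 and Month 6 values of non-returners contribute nothing.

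**4. Size for a within-group mean.** There is no plan figure to reproduce. The documents give no Month 12 return rate, no EAS size and no standard deviation. Let r be the share returning and D the mean change in returners minus that in non-returners.

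- Full-group mean = r × (returner mean) + (1 − r) × (non-returner mean).
- Bias of the returner mean = (1 − r) × D.

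Both inputs are assumed:

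| r | D = 0.03 | D = 0.10 |
|---|---|---|
| 90% | 0.10 × 0.03 = 0.003 | 0.10 × 0.10 = 0.01 |
| 70% | 0.30 × 0.03 = 0.009 | 0.30 × 0.10 = 0.03 |
| 50% | 0.50 × 0.03 = 0.015 | 0.50 × 0.10 = 0.05 |
| 30% | 0.70 × 0.03 = 0.021 | 0.70 × 0.10 = 0.07 |

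For scale, the SAP 1.3.1 formula puts 20/25 against 20/20 at log10(25/20) = 0.097 LogMAR. The largest entry is 0.07/0.097, or about 0.7 of that step. The smallest is 0.003/0.097, or about 0.03 of it.

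**5. Size for a difference between arms.** Bias = (1 − r₁)D₁ − (1 − r₂)D₂. With the same r and D in both arms this is zero. With D = 0.10 in both arms and return of 50% against 70%, it is 0.05 − 0.03 = 0.02 LogMAR.

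**6. Precision.** At a fixed standard deviation, the interval half-width grows by 1/√r relative to full return: 1.05, 1.20, 1.41 and 1.83 at 90%, 70%, 50% and 30%.

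**The case against.** The strongest reply is that this SAP version serves a single purpose. SAP 1 says the interim data are to help design Phase 3. SAP 1.1 says the 12-month visits were requested to give FDA 12-month data. SAP 3.2.3.1 names a Month 12 treatment effect as the target, tests no hypotheses and makes the intervals descriptive. Leading with Month 12 is consistent with that aim, and SAP 1.6 limits its departure to this analysis. This stands. Restoring Month 6 as primary is one option with its own trade-off, not a necessary correction, and no type I error claim is at stake.

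Other parts of the reply also stand. Sites asked patients to return, so attendance reflects site effort as well as patient choice. The SAP already mentions a repeated-measures model. The descriptive tables will show the number of patients at each visit by treatment. What is missing is any comparison with the number due, since the disposition summary in SAP 4.1 counts completion at Month 6 only.

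Three stronger readings are tempting, and the documents do not support them:

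- **That the timepoint was chosen after seeing results.** The trial is open-label and ongoing, but nothing says Month 6 or Month 12 outcomes were examined before the choice. SAP 1.5 places the analyses after the interim database lock.
- **That Month 6 is masked and Month 12 is not.** Protocol 8.1 provides for a masked CDVA observer without tying this to a visit.
- **That poor responders are removed before Month 12 by retreatment.** Protocol 5.4 lets patients exit after Month 6, have a repeat procedure and re-enrol, but gives no criterion or rate for it. The SAP has no rule for the first procedure's Month 12 value in such patients. That gap is real, but its direction is not known.

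**Conclusion.** The point holds as an internal inconsistency together with unaddressed Month 12 non-return. SAP 5.1 ranks Month 12 above Month 6, and no other section declares that. The Month 12 estimates rest on returners only, and the SAP 3.6 assurance of complete primary data is wrong on its own definitions.

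Under the assumed 30–90% return and 0.03–0.10 LogMAR gap, a within-group mean would be off by 0.003–0.07 LogMAR, in an unknown direction. These figures illustrate scale and are not evidence that bias exists. If returners and non-returners change alike, the bias is zero. Between-arm differences are affected only if the return rate or the returner gap differs by arm. The consequence is a possibly misleading input to Phase 3 planning, which is worth correcting before the analysis is run.

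**What to change.** - State one primary timepoint for this analysis in SAP 1.2.1, 1.3.1, 1.6 and 5.1. If it is Month 12, say in 1.6 that the protocol's Month 6 endpoint becomes supportive here.
- Prespecify a repeated-measures model of CDVA change at Months 3, 6 and 12 in all EAS patients as the source of the Month 12 estimate, with the per-visit ANOVA as a sensitivity analysis. Patients with no post-baseline CDVA still contribute nothing and should be counted.
- Report Month 12 return by arm, with patients due for the visit as the denominator, and the Month 6 outcomes of returners and non-returners.
- Correct the SAP 3.6 sentence on missing primary data, and stop describing Month 12 as required in SAP 5.

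The cost is text changes, a small table and one model the SAP already contemplates. The downside is that the model relies on data being missing at random given the observed visits. The returner comparison can inform that assumption but cannot prove it.

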3.2.3.1 Justification for Exclusions

The results of the efficacy analysis are strictly to aid in program development. While the exclusions may limit generalizations with interpretation, they are in place to establish estimates

of a treatment effect at month 12 on the set of patients anticipated for the Phase III protocol. No hypotheses are being tested. Point estimates, standard errors, and confidence intervals are to be used for descriptive purposes only.

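### The per-arm Month 12 confidence intervals, which are the primary quantity, rest on an SD pooled over three arms, and the planned unequal-variance analysis covers only differences between arms

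*SAP*

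**What the plan says.** SAP 5.1 defines the primary measure of efficacy as the "mean change from baseline in LogMAR of Corrected Distance Visual Acuity (CDVA) in the Primary Eye at Month 12 for each treatment group". This is a single-arm mean, not a contrast between arms. The method at every visit analysed is stated thus: "analysis of variance (ANOVA) will be used to obtain point estimates and CIs for the change from baseline in LogMAR CDVA for each group". SAP 5 fixes the confidence level: "Point estimates and 95% confidence intervals (CIs) for the mean changes from baseline within each treatment group will be presented". It names no other method for these intervals.

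SAP 3.3 excludes strata and covariates from the planned analyses, and SAP 1.6 confirms three treatment groups. The model is therefore a one-way ANOVA on treatment.

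The sensitivity analysis in SAP 5.1 gives "separate point estimates and confidence intervals for treatment differences based on a two-sample t-tests for each pairwise comparison will be performed without assuming equal variances". For these t-tests, the SAP adds: "Satterthwaite approximation for degrees of freedom will be used". Their target is the difference between two arms. The only other possibility mentioned is left open, with no variance structure stated: "Other sensitivity analysis such as mixed models repeated measures to account for the longitudinal nature of the data may be considered in an ad hoc" fashion.

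SAP 5.2.1 and 5.2.2 repeat the primary analysis for UCVA and Kmax. Appendix B lists the same analysis tables for patients under 22 years and for those with baseline Kmax of at least 47. On use, SAP 3.2.3.1 says: "Point estimates, standard errors, and confidence intervals are to be used for descriptive purposes only".

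**The concern.** A standard one-way ANOVA has one residual variance. The CI for one arm's mean then depends on the scatter in the other two arms as well as its own. If the arms differ in variability, the interval is too narrow for the most variable arm and too wide for the least variable one. This happens even with equal arm sizes, and coverage does not improve as the sample grows.

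The plan includes an unequal-variance analysis for the pairwise differences but not for the per-arm means, which it names as primary. With no hypothesis being tested, the estimates and their stated precision are the product of this analysis. A nominal 95% interval that is really an 89% or a 99% interval is a defect in that product, although a modest one.

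**Working it through.** **Inputs from the documents.** Three arms (SAP 1.1.1, 1.6); no covariates (SAP 3.3); 95% intervals (SAP 5), taken as two-sided. The documents give no SD of change, no efficacy-set size and no planned interval width, so there is no figure of the plan's own to reproduce.

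**Assumptions.** Normally distributed changes; 100 patients per arm; three sets of arm SDs in logMAR: equal, 0.18/0.20/0.22 and 0.15/0.20/0.25. Which UVA group would be the more variable is not known, so the arms are ordered only by SD.

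**Formulas.**
- ANOVA interval for arm i: mean ± t(0.975, N−3) × √(MSE/n_i), where MSE = Σ(n_i−1)s_i² / (N−3).
- Own-SD interval: mean ± t(0.975, n_i−1) × s_i/√n_i.
- Approximate coverage of the ANOVA interval: 2Φ(t(0.975, N−3) × pooled SD / SD_i) − 1.

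With 100 per arm, t(0.975, 297) = 1.968 and t(0.975, 99) = 1.984.

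**Mild pattern, 0.18/0.20/0.22.** Pooled SD = √((0.0324 + 0.0400 + 0.0484)/3) = 0.2007.
- Least variable arm: 1.968 × 0.2007/0.18 = 2.194, coverage 97.2%.
- Middle arm: 1.968 × 0.2007/0.20 = 1.975, coverage 95.2%.
- Most variable arm: 1.968 × 0.2007/0.22 = 1.795, coverage 92.7%.

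**Stronger pattern, 0.15/0.20/0.25.** Pooled SD = √((0.0225 + 0.0400 + 0.0625)/3) = 0.2041. The ANOVA half-width is the same in every arm: 1.968 × 0.2041/10 = 0.040.

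| Arm SD | Own-SD half-width | ANOVA half-width | ANOVA coverage |
|---|---|---|---|
| 0.15 | 1.984 × 0.15/10 = 0.030 | 0.040 | 99.3% |
| 0.20 | 1.984 × 0.20/10 = 0.040 | 0.040 | 95.5% |
| 0.25 | 1.984 × 0.25/10 = 0.050 | 0.040 | 89.2% |

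**Simulation check** (200,000 runs per setting, stronger pattern, 100 per arm). ANOVA coverage was 99.3/95.5/89.1%. Own-SD coverage was 95.0% in the outer arms and 95.1% in the middle one.

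**Dependence on n.** In the most variable arm, simulated ANOVA coverage was 89.2%, 89.1% and 89.0% at 50, 100 and 200 per arm. The coverage error stays; the absolute gap in half-width shrinks roughly as 1/√n.

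**Equal SDs.** Both methods hold 95%. The price of own-SD intervals is then the ratio of t-quantiles: 1.984/1.968 = 1.008 at 100 per arm (0.8% wider), and t(19)/t(57) = 2.093/2.002 = 1.045 at 20 per arm (about 4.5% wider).

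**The case against.** Several points on the other side stand.

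- **Nothing shows that the variances differ.** The arms are randomized from one population, stratified by site and indication, and two of the three share the same total UVA dose. The stronger pattern assumes a variance ratio of (0.25/0.15)² = 2.8. The mild pattern produces only a small error.
- **The absolute gap is small.** In the stronger pattern it is 0.050 − 0.040, about 0.01 logMAR. By the conversion in SAP 1.3.1, 20/20 and 20/25 differ by 0.097 logMAR, so the gap is about a tenth of that acuity step.
- **Use is descriptive.** SAP 3.2.3.1 tests no hypothesis, and no decision rule depends on the coverage of a single-arm interval.
- **Pooling is inferred.** The SAP does not say that it pools. But pooling is what a standard ANOVA does, no group-specific variance is specified, and the t-tests are marked out as the analysis that does not assume equal variances.

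A reader might go further and infer that the pooled intervals would mislead the choice of UVA setting. The documents do not support that: point estimates do not change, and differences between settings already get Satterthwaite intervals. A reader might also infer that the Phase 3 SD would be misjudged. SAP 3.1 plans n, mean and SD by treatment, and Appendix B has a CDVA summary table (4.1.1) separate from the ANOVA table. If that table shows the change, each arm's own SD is visible and the own-SD interval can be rebuilt. Nor does the plan express doubt about equal variances. SAP 1.6 calls the pairwise t-tests supportive, and two-sample t-tests were already the protocol's method (section 8.0).

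These points limit the harm. They do not give the primary quantity an interval that is valid when the SDs differ.

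**Conclusion.** The point holds as a minor, conditional weakness. Under the standard reading of ANOVA, the prespecified interval for each arm's Month 12 mean change is correct only if the three arms share one SD, and the planned unequal-variance analysis does not reach that quantity. The same applies to UCVA and Kmax.

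The size depends wholly on SDs that the documents do not give. With an assumed 100 per arm, coverage in the least and most variable arms runs from about 97% and 93% under the mild pattern to about 99% and 89% under the stronger one. If the SDs are equal there is no error. The finding concerns the stated precision of single-arm means. It does not extend to the point estimates, the Satterthwaite comparisons, the selection of a UVA setting or the SD carried into Phase 3.

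**What to change.** In SAP 5.1, and so in 5.2.1 and 5.2.2, state that each arm's CI and SE for mean change are computed from that arm's own SD with n−1 degrees of freedom. Equivalently, fit the same linear model with a separate residual variance per arm. Keep the ANOVA and the Satterthwaite t-tests for the pairwise differences.

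The change is one sentence in the SAP and one programming option. Its price is slightly wider intervals if the SDs are equal: about 0.8% at 100 per arm, and about 4.5% if a subgroup has only 20 per arm.
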